4.66 Survival Analyses

Survival analyses will be carried out on the time to event outcomes using Kaplan-Meier plots and lifetable analyses.

4.7 Missing or Incomplete Data

Every effort will be made to minimize the amount of missing data. Recognizing the difficulty of avoiding some missing data, however, data imputation methods with sensitivity imputation analyses will be carried out. Safety endpoint analysis will include all subjects experiencing at least one component for the safety endpoint or with follow-up to the lower limit of the follow-up window for each time point, i.e., the denominator will be adjusted for missing data. Subjects with missing effectiveness data for target lesions (MLD at the conclusion of atherectomy) will be assumed to have missing data at random and will be imputed by random selection with replacement of data from target lesions with post-atherectomy measurements. The robustness of the multiple imputation outcome will be tested with a tipping point analysis encompassing all possible imputation outcomes.

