7.6. Missing Data

Every effort will be made to minimize the amount of missing data. Recognizing the difficulty of avoiding some missing data, however, data imputation methods with sensitivity imputation analyses will be pre-specified in the Statistical Analysis Plan. Subjects with missing effectiveness data for target lesions (MLD at the conclusion of atherectomy) will be assumed to have missing data at random and will be imputed by random selection with replacement of data from target lesions with post-atherectomy measurements. The robustness of the multiple imputation outcome will be tested with a tipping point analysis encompassing all possible imputation outcomes.

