8.2. Point of Enrollment

Subjects will be consented prior to the index procedure, at a point where the anatomic eligibility criteria may be unknown to the Investigator. Enrollment in the study will occur at the point of insertion of the study device into the vasculature, when the device enters the portion of the sheath/guide that resides within the subject's arterial tree.

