9.3. Protocol Deviations

A protocol deviation is the non-adherence to or divergence from the protocol-specific study procedures. For example, violations of the inclusion and exclusion criteria, deviations from the schedule of required follow-up assessments, improper or lack of consent, and lack of IRB approval, would all be considered protocol deviations. A protocol deviation undertaken to protect the life or physical well-being of the patient in an emergency is a special circumstance that must be reported to the Sponsor and the reviewing IRB within 5 working days. The Sponsor must report the deviation to the FDA within 5 working days after the Sponsor learns of the deviation. No other type of prospective protocol deviation is permitted without prior approval. A record of all protocol deviations will be maintained and reviewed throughout the conduct of the study. The Sponsor will address deviations and take appropriate corresponding action. Continued non-compliance with the study protocol may lead to termination of the Investigator's participation in the study.

Subject eligibility for the study is determined by site-measured anatomic criteria; not by core laboratory values. For this reason, enrollment of subjects with core laboratory-determined anatomic measurements on the baseline, pre-interventional angiogram will not be protocol deviations.

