2. ENDPOINT DEFINITIONS

2.1 Primary Safety Endpoint

The primary safety endpoint is a composite endpoint triggered by the occurrence of any five categories of events through 30 days after the index procedure¹. These events are the following:

1. All-cause mortality- Death from any cause, from the point of enrollment through 30 days.
2. Clinically-driven TLR- Any revascularization of the target lesion that occurs after the subject has left the procedure room following the index procedure. TLR do not include adjunctive interventions performed during the index procedure, whether planned or for failed atherectomy or for complications of atherectomy. TLRs are considered to be clinically-driven when they occur as a result of restenosis >50% diameter reduction as measured angiographically or by duplex ultrasound (occlusion or stenosis with Peak Systolic Velocity Ratio >2.4)².
3. Perforation of the target vessel- Imaging evidence (standard contrast angiography, computed tomography angiography or open surgical/pathology visualization) of target vessel perforation from any cause. For angiography and CTA, perforation is defined by contrast extravasation outside of the adventitia.
4. Clinically- significant distal embolization- Target limb embolization documented on core laboratory- assessed angiography or with open surgery/pathology, accompanied by symptoms referable to the involved vascular bed.
5. Major amputation- Amputation of the target limb that results in limb shortening; i.e. is performed at or above the level of the malleoli.

The composite endpoint and each individual component are all subject level endpoints.

¹ The index procedure is considered to occur on day 0; the first post-procedure day is day 1, and so on. The 30-day time point includes any events with a start date prior to 11:59PM on day 30.

² If an angiogram and a duplex ultrasound imaging study are discordant within any 30-day period, the angiographic results will supersede the duplex findings.

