3. ANALYSIS POPULATION

The point of enrollment in this study occurs when a study device first enters a subject's vasculature.⁴ The following populations will be analyzed in the study:

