3.2 Per Protocol (PP) Analysis

The PP analysis will be performed on target lesions with core laboratory determined RVD falling within the pre-specified anatomic eligibility criteria of ≤ 4.0 mm. The effectiveness endpoints will be determined using the PP analytic subset to exclude lesions where the largest bore (2.0 mm) study device is less than 50% of the RVD. The per protocol population has no other pre-specified inclusion/exclusion violations(s) or requirement for adequate follow-up (or a loss of patency).

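### The missing-data rule for technical success imputes every unmeasured target lesion as missing at random, including one left unmeasured because the device or procedure failed

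*SAP*

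**What the plan says.** **The rule.** SAP 4.7 covers target lesions with no minimum luminal diameter (MLD) at the end of atherectomy. Such data "will be assumed to have missing data at random and will be imputed by random selection with replacement of data from target lesions" that do have a measurement. Protocol 7.6 has the same rule: data "will be imputed by random selection with replacement of data from target lesions with post-atherectomy measurements". Neither text distinguishes reasons for the gap, and neither says whether the value drawn is the MLD, the percent stenosis or the success flag.

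**The safeguard.** SAP 4.7 adds: "The robustness of the multiple imputation outcome will be tested with a tipping point analysis encompassing all possible imputation outcomes". SAP 4.5 declares success on effectiveness when the one-sided 97.5% lower limit exceeds 76%, and does not refer to that analysis.

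**Which lesions count.** SAP 4.3 analyses all investigator-identified target lesions in the per-protocol (PP) set, per lesion. SAP 3.2 defines that set by core-laboratory reference vessel diameter (RVD) and, as I read it, adds no other exclusion. Protocol 9.3 refers to "core laboratory-determined anatomic measurements on the baseline, pre-interventional angiogram", so an RVD can exist for a lesion with no post-atherectomy image.

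**When a subject is in.** Protocol 8.2: "Enrollment in the study will occur at the point of insertion of the study device into the vasculature". SAP 3 agrees. That point comes before the device has reached a lesion.

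**Failures foreseen.** SAP 2.1, when defining revascularization events, leaves out adjunctive interventions "whether planned or for failed atherectomy or for complications of atherectomy". Protocol 8.3 foresees conversion to open surgery after treatment failure, and Protocol 8.8 foresees aborted procedures. None of these passages gives the lesion an effectiveness outcome.

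**Reasons for missing data.** Protocol 12.4.1 already requires case report forms (CRFs) to document why data are missing.

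**The concern.** Missing at random is a fair working assumption for an angiogram that was lost or could not be read. It is not fair when the measurement is absent because atherectomy failed, since the gap is then caused by the outcome. The donors are lesions that were treated and imaged. Drawing from them gives a failed attempt roughly a four-in-five chance of being counted as a success.

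The error runs in one direction: it raises observed technical success and the chance of wrongly passing the 76% goal. The endpoint is one of two that must both be met. The study is single-arm and open-label, so a scoring rule for these lesions chosen after the results are known would be hard to defend.

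**Working it through.** **1. The plan's own figure.** SAP 3.3 gives a goal p0 = 0.76, an anticipated rate p1 = 0.86, one-sided alpha 0.025, 90% power and 165 lesions. The normal approximation is

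n = [(1.960·√(0.76·0.24) + 1.282·√(0.86·0.14)) / 0.10]² = 164.3, so 165.

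This reproduces the plan. For the exact binomial test at 165 lesions, the smallest x with P(X ≥ x | 165, 0.76) ≤ 0.025 is 137 (83.0%). Its alpha is 1.87%, and its power at 86% is 88.5%.

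**2. Assumptions for the illustration.** Neither the number of unmeasured lesions, k, nor the share of them that are true failures, f, is in the documents. I take k = 3, 5, 8 and f = 1, 0.5, 0.25. Lesions are independent, and true success over all 165 is exactly 76%.

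**3. Formulas.** For the overall rate to stay at 76%, measured lesions must succeed at

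p = 0.76·165 / [(165 − k) + k(1 − f)].

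Measured successes are X ~ Bin(165 − k, p). Imputed successes are Bin(k, X/(165 − k)). The trial passes if the total is at least 137. The upward bias is p − 0.76. Example for k = 5, f = 1: p = 125.4/160 = 0.784, a bias of 2.4 points.

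**4. False-pass chance under the rule as written** (1.9% with nothing missing)

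| Share that are true failures | k = 3 | k = 5 | k = 8 |
|---|---|---|---|
| All (bias 1.4, 2.4, 3.9 points) | 5.1% | 9.1% | 19.3% |
| Half | 3.3% | 4.6% | 7.3% |
| A quarter | 2.6% | 3.2% | 4.2% |

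**5. The same cases under other scoring.** With every missing lesion counted as a failure, and all of them true failures, the false-pass chance is 1.6%, 1.4% and 1.1%. With only the true failures scored as failures and the rest imputed, it is 1.1% to 2.0% in all nine cells.

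**6. Sensitivity to the method.**
- *More lesions.* 121 subjects at 1.5 lesions each gives about 181. The threshold becomes 150 (alpha 1.6%), and the top row becomes 4.3%, 7.7% and 16.3%.
- *Multiple imputation.* With 20 imputations, Rubin's rules and a Wald limit, the baseline is 2.9%. It rises to 13.1% when 3% of lesions (about 5) are unmeasured failures and 26.7% when 5% (about 8) are.
- *Clustering.* Simulation used 110 subjects, half with two lesions, within-subject correlation 0.2 to 0.4, and a cluster-robust limit standing in for GEE. The baseline is 3.6–3.8%, and the top row is about 9%, 13–14% and 25–26%.
- *Quantity drawn.* If a donor MLD is divided by the recipient lesion's own RVD, fewer draws succeed. Assuming RVD uniform on 2–4 mm and residual stenosis normal with SD 8–15 points, the top row falls to 4.2–4.5%, 7.0–7.7% and 13.5–15.5%.

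**7. At the planned rate.** Suppose measured lesions succeed at 86% and the unmeasured ones are failures. With 5 unmeasured, about 138 of 160 measured lesions succeed, and the trial passes under either scoring. With 8, about 135 of 157 succeed. Imputation expects about 142 successes and passes, while failure scoring gives 135 and does not. The change comes at about 7 lesions.

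**The case against.** - *The tipping-point analysis covers this.* It spans all imputation outcomes, so it must include the case where every missing lesion failed, and step 5 shows that this case would expose most false passes. A reader might infer that the plan hides the problem or has no safeguard. It does not hide it. What stands is narrower: the primary estimate and success rule use the imputed values, and nothing says what follows if the result tips.
- *Such lesions may never occur.* This is right. The endpoint definition calls for a post-atherectomy angiogram before adjunctive therapy, and the procedure is done under angiographic guidance. A failed lesion with a readable image is measured and unaffected. The passages on failure, conversion and abortion were written for other purposes and do not say that an image will be absent. The Core Lab Manual, which might address this, is not among the documents.
- *The reason for absence will not be known.* A reader might infer this because the Treatment CRF list in Protocol 8.3 has no item for the post-atherectomy angiogram. Protocol 12.4.1 does not support that inference, since it requires reasons for missing data. The Treatment CRF also records device issues, adjunctive therapy and additional procedures. The gap is in the analysis rule, not in data collection.
- *The largest figure is extreme.* 19.3% needs 8 of 165 lesions unmeasured, all true failures, and true success exactly at the goal. With 3 to 5 unmeasured and a quarter to a half true failures, the range is 2.6% to 4.6%.

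**Conclusion.** The concern holds as a fault in the stated rule. Followed as written, SAP 4.7 and Protocol 7.6 would credit an attempted lesion, unmeasured because of device or procedural failure, at about the success rate of measured lesions.

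The size is conditional. Each unmeasured true failure raises the estimate by about half a percentage point. In the illustration, the false-pass chance goes from 1.9% to between 2.6% and 19.3%, depending on assumed k and f. Other analysis methods shift the figures either way but not the direction.

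A reader might infer that the trial's technical success will be inflated. The documents do not support that, because the number of such lesions is unknown and may be zero. It should be fixed because it concerns a primary endpoint and costs little to settle in advance. The differing RVD bounds in SAP 4.3, against SAP 3.2 and Protocol 7.3, are a separate matter and carry no weight here.

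**What to change.** In SAP 4.7 and Protocol 7.6:

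1. Score as a technical failure any attempted PP target lesion with no post-atherectomy measurement because of device or procedural failure. Define attempted as study device introduced to treat that lesion.
2. Limit missing-at-random imputation to lost or unreadable angiograms, and state which quantity is drawn.
3. Use the missing-data reason already required by Protocol 12.4.1, classified under a rule fixed before results are seen. The rule should also cover undetermined reasons.
4. Report the all-missing-as-failure scenario of the planned tipping-point analysis beside the primary result.

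**Cost.** This is wording in two documents and a few classifications. Observed technical success may be slightly lower. When the reason is known, power at a true 86% is not reduced: about 88–92% for k = 3 to 8, against 88.5% with nothing missing.

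The treatment of undetermined reasons is a choice with a price. If 3, 5 or 8 truly lost images had no recorded reason and were scored as failures, power would be P(Bin(165 − k, 0.86) ≥ 137) = 74%, 61% or 38%. The reason should therefore be recorded at the index procedure.

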5. ENDPOINT ALGORITHMS

5.1 Safety Endpoints

For missing values, an adjustment to the denominator will be made based on the amount of evaluable data for safety-endpoints.

Safety denominator adjustment: For each visit (or reporting time point), the event rate will be calculated as the number of subjects with certain event term over the number of evaluable subjects. The evaluable subjects at each reporting time point include all subjects who are enrolled by the snapshot date and

- 1) Had an event within (on or before) the reporting cutoff days, or
- 2) Had a follow-up at or after the lower limit of the reporting window, or
- 3) The withdrawal consent date/recorded lost-to-follow-up date at or after the lower limit of the reporting window

‘Days to event’ (date of earliest event – date of index procedure) and ‘Days to last contact’ (date of last contact – date of index procedure) are usually used for the determination of the eligibility of the ‘evaluable subject’. The last contact date will be calculated based on the information gathered from all available dates during the follow-ups.

The ‘Reporting Cutoff Days’, ‘Lower limit of the Reporting Window’ and the correspondent visits are as the following:

Visit	Reporting Cutoff Days	Lower Limit of the Reporting Window (days post-index procedure)
1-month	30 days post-index procedure	Days to last contact: 23
6-month	180 days post-index procedure	Days to last contact: 166

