7.9. Sample Size

The PG of 80% has been established for the primary safety endpoint, based on a one-sided 97.5% exact binomial test. The 30-day MAE rate is anticipated to be approximately 9%. Under these assumptions, the required sample size to achieve a level of 90% power is 110 subjects (**Table 4**). Assuming 10% attrition over 30 days, initial enrollment of 121 subjects is necessary.

A PG of 76% has been established for the primary effectiveness endpoint. Anticipating an actual technical success rate of approximately 86%, and based upon a one-sided 97.5% exact binomial test, the required sample size to achieve a level of 90% power is 165 target lesions. Assuming a 1.5 ratio of subjects to treated target lesions, approximately 110 subjects will be necessary (**Table 5**). Since the primary effectiveness endpoint is determined at the time of the index procedure, no attrition has been taken into account.

ⁱ The TALON publication reported the results in 1258 target lesions, among which 132 required preliminary balloon dilatation to deliver the device and technical success ($\leq 50\%$ residual stenosis after atherectomy) was not achieved in 54 lesions. Technical success was calculated assuming there was no overlap between these cases; i.e. technical success was achieved in 1072 (1258 – 132 - 54) lesions.

Table 4. Sample Size – Primary Safety Endpoint

Primary Safety Endpoint	
Performance goal	80%
Anticipated freedom from MAE	91%
Significance level	.025
Statistical test	One-sided exact binomial test
Desired power level	90%
Required sample size prior to 10% 30-day attrition rate	110
Required sample size after attrition adjustment	121

Table 5. Sample Size – Primary Effectiveness Endpoint

Primary Effectiveness Endpoint	
Performance Goal	76%
Anticipated technical success rate	86%
Significance level	.025
Statistical test	One-sided exact binomial test
Desired power level	90%
Required sample size (target lesions)	165
Estimated subjects required for required number target lesions*	110

* Assumes 1.5 target lesions treated per subject; a ratio calculated from the studies in the atherectomy literature review

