3.3 Sample Size Consideration

This study will enroll up to 121 subjects at up to 18 investigational sites and the sample size estimation was based on binomial hypothesis testing of a single proportion.

The performance goal (PG) of 80% has been established for the primary safety endpoint. Sample size estimation was based on a one-sided 97.5% exact binomial test. The 30-day

⁴ This point is defined as entry of the study device into the access sheath/guide at the level where the sheath/guide enters the subject's body.

MAE rate is anticipated to be approximately 9%. Under these assumptions, the required sample size to achieve a level of 90% power is 110 subjects (Table 1). Assuming 10% attrition over 30 days, initial enrollment of 121 subjects is necessary.

A PG of 76% has been established for the primary effectiveness endpoint. Anticipating an actual technical success rate of approximately 86%, and based upon a one-sided 97.5% exact binomial test, the required sample size to achieve a level of 90% power is 165 target lesions. Assuming a 1.5 ratio of subjects to treated target lesions, approximately 110 subjects will be necessary (Table 2). Since the primary effectiveness endpoint is determined at the time of the index procedure, no attrition has been taken into account.

Table 1. Sample Size – Primary Safety Endpoint

Primary Safety Endpoint	
Performance goal	80%
Anticipated freedom from MAE	91%
Significance level	.025
Statistical test	One-sided exact binomial test
Desired power level	90%
Required sample size prior to attrition (subjects) adjustment*	110
Required sample size after attrition rate adjustment	121
*Assumes 10% 30-day attrition	

Table 2. Sample Size – Primary Effectiveness Endpoint

Primary Effectiveness Endpoint	
Performance Goal	76%
Anticipated technical success rate	86%
Significance level	.025
Statistical test	One-sided exact binomial test
Desired power level	90%
Required sample size (target lesions)	165
Estimated subjects required for required number target lesions*	110
*Assumes 1.5 target lesions treated/subject; ratio calculated from atherectomy literature review.	

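### The evaluable-subject rule makes safety attrition non-neutral in either direction, and 110 evaluable subjects give 88.2% exact-test power, not 90%

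*SAP*

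**What the plan says.** SAP 5.1 (Safety Endpoints) defines the reported rate: "the event rate will be calculated as the number of subjects with certain event term over the number of evaluable subjects". A subject is evaluable at a time point on any one of three conditions:

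1. an event on or before the cutoff (day 30 or day 180);
2. a follow-up at or after the lower window limit (day 23 or day 166);
3. a withdrawal date or recorded lost-to-follow-up date at or after that limit.

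The table under this list describes the limit in terms of days to last contact only.

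SAP 4.7 gives a similar rule in other words: "Safety endpoint analysis will include all subjects experiencing at least one component for the safety endpoint or with follow-up to the lower limit". Here too, subjects without enough data are taken out when the rate is calculated.

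SAP 4.66 adds, without naming an endpoint or a reported estimate: "Survival analyses will be carried out on the time to event outcomes using Kaplan-Meier plots and lifetable analyses".

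On sample size, SAP 3.3 sets the safety goal at 80% free from MAE, tests it with an exact binomial test at one-sided 2.5%, and concludes that "the required sample size to achieve a level of 90% power is 110 subjects". Enrolment is then raised to 121 to allow for a 10% loss by day 30. Protocol 7.9 and SAP 3.3 both use a 9% MAE rate, applied unchanged to the subjects who remain.

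**The concern.** The rule treats partial follow-up differently according to outcome. A subject with an event who is then lost stays in the numerator and the denominator. A subject lost event-free before the lower limit leaves the denominator. A subject lost event-free between the lower limit and the cutoff is credited with complete event-free follow-up. The first two together push the rate up, and the third pushes it down.

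This denominator feeds the primary safety test. Perforation and distal embolization, both MAE components, plausibly cluster around the procedure and so before any loss. Protocol 8.8 also creates early event-free loss, because subjects with an aborted procedure need not complete follow-up unless converted to surgery.

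Two things are at stake: the power of the safety test, which was planned as if attrition left the 9% rate untouched, and the accuracy of the 6-month rates of MAE components, MI, minor amputation and TVR.

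**Working it through.** **Inputs from the documents.** Performance goal 80% free from MAE; anticipated 91% (9% MAE); one-sided 0.025, exact binomial; 110 evaluable; 10% attrition over 30 days; 121 enrolled; lower limits day 23 and day 166. The documents do not say when events or losses occur. All timings below are assumptions, with loss taken as unrelated to outcome.

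**Step 1: reproduce the plan's figure.** Normal approximation:

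n = [(1.960·√(0.80·0.20) + 1.282·√(0.91·0.09)) / 0.11]² = 109.4, so 110. Then 110 × 1.10 = 121.

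**Step 2: the exact test at 110.** Success needs at least 97 of 110 event-free (type I error 1.70%; at 96 it would be 3.20%). Power = P(X ≥ 97 | n = 110, p = 0.91) = **88.2%**. The gap from 90% comes from discreteness and owes nothing to the denominator rule. Power is 90.0% at n = 107 and 86.9% at n = 112.

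**Step 3: 121 enrolled, 10% lost before day 23, event-free losses removed.** Let f be the share of events that would precede the loss.

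- Observed events: 0.09 × [1 − 0.10(1 − f)]
- Evaluable and event-free: 0.91 × 0.90 = 0.819
- Expected rate: the first divided by the sum of the two
- Power: exact-test power averaged over the resulting evaluable n

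| f | Expected MAE rate | Power |
|---|---|---|
| 0 (neutral loss) | 0.0810/0.9000 = 9.0% | 88.2% |
| 0.25 | 0.08325/0.90225 = 9.2% | 86.5% |
| 0.5 | 0.0855/0.9045 = 9.5% | 84.6% |
| 1 | 0.0900/0.9090 = 9.9% | 80.7% |

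With losses even over days 1–22 and events even over 30 days, f = 11.5/30 = 0.38, which gives 9.3% and 85.5%. The largest upward shift is 9.9 − 9.0 = 0.9 points.

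**Step 4: other timings, same 121, 9% and 10%.** Each range runs from all events on day 0 to events spread evenly.

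| Loss pattern | Expected MAE rate | Power |
|---|---|---|
| Days 1–22, removed | 9.9% to 9.3% | 80.7% to 85.5% |
| Even over days 0–30 (0.10 × 23/30 = 7.7% before day 23) | 9.7% to 9.2% | 84.0% to 87.5% |
| All on days 23–30 (kept as event-free) | 9.0% to 8.9% | 92.3% to 92.9% |
| Days 1–22, all kept under condition 3 | 9.0% to 8.4% | 92.3% to 95.1% |

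In the last row with even events, the rate is 0.09 × [1 − 0.10 × (1 − 0.383)] = 8.4% on all 121 subjects.

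**Step 5: type I error.** At a true MAE rate of 20%, with loss before day 23 and removal, it is 1.8% (f = 0), 1.05% (f = 0.5) and 0.6% (f = 1), all below 2.5%.

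**Step 6: six months.** No attrition is stated. As illustration only, take an assumed 9% rate with all events before loss. Loss of 20% before day 166 gives 0.09/(0.09 + 0.91 × 0.80) = 11.0%, and 30% gives 0.09/(0.09 + 0.91 × 0.70) = 12.4%. Losses credited as complete follow-up would move the rate the other way.

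**The case against.** A reader might infer that the rule always overstates event rates and that safety power is 80–86% on the plan's own inputs. The documents do not support that.

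- **Timing is not given.** The plan states 10% attrition over 30 days, not before day 23. The 80–86% range needs all of it on days 1–22 and removed.
- **Condition 3 can keep missed-visit subjects.** The first scheduled visit after discharge falls on days 23–37. Protocol 8.8 declares loss only after two contact attempts and a certified letter. A subject who simply misses that visit will usually have a recorded loss date at or after day 23 and so counts as event-free. Read that way, the upward bias disappears or reverses. The table's reference to last contact points the other way, so the text is ambiguous.
- **About 2 points of the shortfall are discreteness**, present with no attrition effect at all.
- **Deaths need not leave the denominator.** It is tempting to say that subjects who die before day 166 drop out of the non-fatal rates. SAP 4.7 keeps anyone with at least one safety component, and death is a component. SAP 5.1 reads as event-specific. The two sections conflict, and neither settles it.
- **The upward bias is conservative.** It costs the sponsor power and does not produce false success. The 6-month rates carry no performance goal.

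All of this stands and limits the point. It does not remove it: the rule still mishandles partial follow-up, in a direction set by unstated timing, while a method that handles it is already planned.

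**Conclusion.** The point holds in a limited form. The evaluable-subject rule can bias the crude safety rate up or down, so attrition is not neutral as the sample size assumes. At 30 days with 10% loss unrelated to outcome, the upward shift is at most about 0.9 points and conservative. The downward shift reaches about 0.6 points (9.0% to 8.4%) in the cases examined, and that direction favours success.

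The stated 90% is not delivered by the named test at 110 evaluable subjects, where power is 88.2%. At 121 enrolled the rule can lower power to about 81% or leave it at 92% or more, so no single figure can be attributed to the plan. At 6 months the direction and size cannot be established from the documents.

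**What to change.** **SAP 5.1 and 4.7**
- Name the Kaplan-Meier estimate at day 180, censored at last contact, as the reported 6-month rate. For non-fatal components use cumulative incidence with death as a competing event. Keep the crude evaluable rate as supportive.
- Report the day-30 Kaplan-Meier MAE estimate beside the primary result, and leave the primary exact test unchanged.
- State whether last contact or the recorded loss or withdrawal date governs evaluability.
- Reconcile the two sections on whether a subject who dies without the event in question stays in the denominator.

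**SAP 3.3 and Protocol 7.9**
- Restate exact-test power as about 88% at 110 evaluable subjects.
- Give the power range under the evaluable-subject rule with its timing assumptions, not one figure.

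The cost is wording. The Kaplan-Meier analyses are already planned, and the performance goal and enrolment do not change. The stated power becomes slightly less favourable.
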